#### 4.3.1. **Primary Outcome Measures**:

- 1. Feasibility: Percentage of subjects for whom administration of IVIG is feasible, defined as the successful administration (at least 80% of each dose) of the 3 doses of IVIG at the prescribed times through peripheral IV lines or central lines if already in place for clinical indications.
- 2. Acceptability: Percentage of subjects for whom the study is acceptable, defined as the ability of the subject's family or guardian to allow intravenous line placements, blood draws, and other study procedures for the study subjects.
- 3. Safety and tolerability measures:
  - a. Percentage of subjects with any serious adverse events (SAEs),
  - b. Percentage of subjects with any level 3, 4, or 5 toxicity (per NCI CTEP grading system [http://www.eortc.be/services/doc/ctc/ctcaev3.pdf], and
  - c. Percentage of subjects with other expected adverse events (such as allergic reactions, irritability, fluid volume problems, IV infiltration and aseptic meningitis).

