#### 4.12.4 Subjects receiving a Liver Transplant

If a subject receives a liver transplant prior to 360 days post-HPE, any remaining IVIG infusions will be discontinued and the subject will continue to be followed only for serious adverse events. Serious adverse events will be reported as per section 7.2 and 7.3 of the protocol.

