# 5.2.2. Preliminary Efficacy (Activity).

The use of concurrent placebo or active control subjects was considered for this study, however it is not feasible to treat infants in a research study with an IV placebo (normal saline) and the availability of robust patient-level data for historical controls from another ChiLDREN study were felt to justify the bias issues inherent in the use of historical controls.

Placebo subjects from the ChiLDREN START (Steroids in Biliary Atresia Randomized Trial) study will be used as a historical comparative group to compare with subjects in this study who receive IVIG. Approximately 70 subjects in START received placebo from 2006-2011, but were otherwise treated similarly to the subjects in the current trial, except they received no IVIG. It is anticipated that the START randomized double-blind study will be unblinded in early 2013. With the anticipated length of this IVIG study (24-30 months enrollment and 12 months of follow-up), we will be able to use the START placebo subjects as the comparative group.

A one-sided testing strategy was chosen given that we are only interested if IVIG improves the preliminary measures of efficacy.

Hypothesis 2a states that treatment with IVIG will improve the probability of an infant having good bile flow 90 and 180 days after HPE for BA as evidenced by total serum bilirubin concentration. The primary endpoint for this hypothesis is the proportion of subjects who survive 180 days after HPE with both their native liver and serum total bilirubin <1.5 mg/dL at 180 days after HPE. Based on the ChiLDREN PROBE prospective study, approximately 51% of BA subjects who had an HPE before 4 months of age had good bile drainage at 6 months following the HPE procedure, as determined by a serum total bilirubin level <1.5 mg/dL and survival with their native liver. We anticipate the same improvement in the placebo subjects in the ChiLDREN START study.

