## 7.2. Adverse events (AE) and serious adverse event (SAE)

#### 7.2.1. Adverse events (AE) – Overview

IVIG has not been used in infants with BA following HPE to our knowledge. However, IVIG has been used to treat immune deficiencies, Kawasaki disease, neonatal hemochromatosis and idiopathic thrombocytopenic purpura (ITP) in infants and young children previously, and has been tested in small preterm infants as a therapy to reduce the risk for infection and sepsis. In this study, we will monitor for potential adverse effects appropriately at each scheduled visit. Patients will be followed until complete/adequate resolution of an adverse event is documented. We will continue the evaluation of adverse events if a subject withdraws or is prematurely discontinued from participation in the study for any reason. The list of potential expected adverse effects was developed based on information from the package insert of IVIG and reviews of the published clinical trials of IVIG in the diseases mentioned above (45-46). Notably, some of the potential adverse effects of IVIG may also be present in infants with BA due to the natural progression of disease to biliary cirrhosis, such as fever, rashes, and impaired response to routine immunizations. Therefore, it is important in this study that the frequency, severity and seriousness of adverse effects, as well as their likely causality, be assessed in subjects receiving study medication.

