#### 7.2.2. Grading of AEs

An AE is any unfavorable or unintentional sign (including abnormal laboratory findings), symptom, or disease temporally associated with the use of a medicinal product, whether or not considered related to the medicinal product. Grading of AEs will be based on the National Cancer Institute-Common Terminology Criteria for Adverse Events. Severity of AEs is outlined below:

- Grade 1: Mild adverse event
- Grade 2: Moderate adverse event
- Grade 3: Severe adverse event
- Grade 4: Life-threatening or disabling adverse event
- Grade 5: Death related to adverse event

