#### 7.2.3. Serious Adverse Events (SAE) or Serious Suspected Adverse Reaction

#### Serious Adverse Event or Serious Suspected Adverse Reaction

An adverse event or suspected adverse reaction is considered "serious" if, in the view of either the investigator or sponsor, it results in any of the following outcomes:

- Death,
- A life-threatening adverse event
- Inpatient hospitalization or prolongation of existing hospitalization
- A persistent or significant incapacity or substantial disruption of the ability to conduct normal life functions
- A congenital anomaly/birth defect.

Important medical events that may not result in death, be life-threatening, or require hospitalization may be considered serious when, based upon appropriate medical judgment, they may jeopardize the patient or subject and may require medical or surgical intervention to prevent one of the outcomes listed in this definition. Examples of such medical events include allergic bronchospasm requiring intensive treatment in an emergency room or at home, blood dyscrasias or convulsions that do not result in inpatient hospitalization, or the development of drug dependency or drug abuse. The term SAE is not intended as a measure of severity or intensity.

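### Primary safety outcome 3a, and 3b unless toxicity there means IVIG-related, are all-cause single-arm percentages with no stated window; as analysed they do not separate IVIG harm from biliary atresia events

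*Protocol*

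**What the plan says.** Section 4.3.1 lists three safety and tolerability measures among the primary outcomes:

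- 3a: "Percentage of subjects with any serious adverse events (SAEs".
- 3b: "Percentage of subjects with any level 3, 4, or 5 toxicity".
- 3c: "Percentage of subjects with other expected adverse events (such as allergic reactions, irritability, fluid volume problems, IV infiltration and aseptic meningitis".

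No time window is given for any of them. Section 7.2.2 defines an adverse event "whether or not considered related to the medicinal product", and section 7.2.3 lists "Inpatient hospitalization or prolongation of existing hospitalization" among the criteria for seriousness. Table 3 collects interval adverse events at every visit to day 360. Section 6.1.3 limits IVIG to the first 60 days of a 360-day participation. After a transplant, section 4.12.4 says "the subject will continue to be followed only for serious adverse events". Section 6.1.2 allows a further 6 months after enrollment for primary outcome follow-up.

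The protocol recognises the overlap between drug and disease. Section 7.2.1 notes that "some of the potential adverse effects of IVIG may also be present in infants with BA due to the natural progression of disease" and asks for likely causality to be assessed. Section 5.3 (Aim 1) nevertheless plans only a point estimate and a one-sided 90% Clopper-Pearson lower bound for the safety parameters, in the treated infants alone. The START placebo group is the comparator for Aims 2 and 3; section 5.2.2 justifies that choice by "the availability of robust patient-level data for historical controls from another ChiLDREN study".

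**The concern.** An infant who is transplanted, or who is admitted with cholangitis for the parenteral antibiotics foreseen in section 4.6, meets the any-SAE outcome whether or not IVIG played a part. The protocol states no exemption for expected disease events. About 300 of the 360 days over which events are collected fall after the last planned infusion.

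These percentages belong to the primary aim and will inform whether a larger trial follows. A high value could be read as toxicity when it is disease, and a real excess could be hidden inside a large and unknown background. The planned lower bound does not help a safety conclusion, because limiting a harm rate requires an upper bound. The open window adds a further choice: a count over the infusion period, 6 months or 360 days could give three different answers to the same primary question.

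**Working it through.** **1. Does the protocol fix a window or an attribution rule?**

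- Window: section 4.3.1 states none. Table 3 and section 6.1.3 imply 360 days. Section 6.1.2 implies about 6 months for primary outcomes and treats the 360-day outcomes as secondary. These do not agree.
- Attribution, 3a: none, given the words of the outcome and the definition in section 7.2.2.
- Attribution, 3b: unclear. Section 4.4.5 mentions grade 3 to 5 toxicity and SAEs together with evidence of attribution to IVIG, which does not settle whether the word toxicity alone implies attribution.
- Attribution is available: section 7.2.1 asks for it, sections 4.4.5 and 4.12.3 use it to stop IVIG, and section 7.3 uses it for expedited reporting.

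**2. The plan's own figures (sections 5.2.1 and 5.2.2).**

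- Chance of at least one event, 1 − (1 − p)^n, for n = 23 / 29: p = 0.20 gives 99.4% / 99.9%; p = 0.10 gives 91.1% / 95.3%; p = 0.05 gives 69.3% / 77.4%. The plan states above 98%, 91 to 95% and 69 to 77%.
- Exact one-sample test of 40% or higher at a true 20%: reject at 5 or fewer of 23 (power 69.5%) or 7 or fewer of 29 (79.0%). The plan states 70% and 79%.
- One-sided 10% Fisher test, 76.5% versus 51%: 74.3% with 23 versus 56 and 82.2% with 29 versus 70. The plan states 74% and 82%.

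The plan's arithmetic is sound. The issue is what the outcomes count.

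**3. What the single-arm percentage can show.** The documents give no background SAE rate, so the following is an assumption. With background b and an IVIG-caused SAE in 10% of infants independently, the total is b + (1 − b) × 0.10:

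| Assumed b | Total with IVIG effect |
|---|---|
| 30% | 37% |
| 50% | 55% |
| 70% | 73% |
| 80% | 82% |

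If 15 of 29 infants (51.7%) have an SAE, the one-sided 90% Clopper-Pearson bounds are 38.4% (lower) and 64.9% (upper). Both 50% (no IVIG effect) and 55% lie well inside. With 12 of 23 (52.2%) the bounds are 37.0% and 67.0%.

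**4. What an attributed percentage would show.** With 0 of 29 infants having an IVIG-attributed SAE, the one-sided 90% upper bound is 1 − 0.10^(1/29) = 7.6%; with 0 of 23 it is 9.5%. With 3 of 29 (10.3%) the upper bound is 21.6%. The lower bound, which is what the plan asks for, is 3.9%; it says only that the rate is not smaller than that.

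**5. What a START contrast would show.** At rates near 50%, the one-sided 90% upper bound on the difference lies z × √(p(1 − p)(1/n₁ + 1/n₂)) above the estimate, with z = 1.2816:

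- 29 versus 70: 1.2816 × √(0.25/29 + 0.25/70) = 1.2816 × 0.1104 = 0.142.
- 23 versus 56: 1.2816 × √(0.25/23 + 0.25/56) = 1.2816 × 0.1238 = 0.159.

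For a 10-point excess over an assumed background of 30 to 80%, a one-sided 10% Fisher test has 24 to 29% power with 23 versus 56, and 28 to 37% with 29 versus 70. The contrast can place the IVIG percentage against a background. It cannot firmly confirm or exclude a moderate excess.

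**The case against.** The strongest reply is that the protocol separates drug from disease by other means. Causality is assessed, an independent Medical Safety Officer reviews every SAE, attribution governs discontinuation and expedited reporting, and outcome 3c counts mainly infusion-related events. Single-arm percentages are usual in a phase 1/2A trial sized for precision, and related/unrelated tables are often left to the SAP.

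Much of this stands. A reader might infer that IVIG harm cannot be separated from biliary atresia at all in this trial; the documents do not support that. The point is narrower: attribution does not enter 3a or, explicitly, 3b, and section 5.3 itself fixes their analysis. The outcome definition and its window belong in the protocol.

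Three other tempting readings also fail:

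- Taking 100% − 68% = 32% from section 5.2.2 as a death or transplant rate. The 68% also requires bilirubin below 1.5 mg/dL, so the remainder includes jaundiced infants alive with their native liver, and it is measured at 12 months of age rather than 360 days after HPE.
- Computing power against the 40% null under a high background. Section 5.2.1 calls that level arbitrary and illustrative, and section 5.3 plans no such test.
- Treating SAE follow-up after transplant as a major inflation of 3a. If the transplant admission already counts as an SAE, later SAEs in that infant do not change a subject-level percentage.

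A START comparison has its own weakness. START was double-blind and this trial is open-label, and the similarity claimed in section 5.2.2 concerns treatment, not how adverse events were recorded. The safety conclusion should not rest on it.

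**Conclusion.** The concern holds in limited form. Outcome 3a, and 3b unless toxicity means IVIG-related, are all-cause percentages with no stated window, collected to day 360 and analysed in one arm with a bound on the wrong side for safety. As analysed they do not separate IVIG harm from disease events, although causality is already assessed and an external control group is already in use for efficacy.

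The size cannot be stated exactly, because no background SAE or grade 3 to 5 rate is given; it would therefore go too far to say that the percentage will mostly measure natural history. Under the assumed 50% background, a 10% independent IVIG effect moves the rate by 5 points, against one-sided bounds that each lie about 13 points from an observed 52% (15/29). The value of a START contrast rests on comparable recording and grading of adverse events, which the documents do not describe.

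**What to change.** In section 4.3.1 and section 5.3 (Aim 1):

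1. State the window for 3a and 3b, for example the infusion period and the full 360 days, and reconcile it with the 6-month primary follow-up in section 6.1.2. Say whether toxicity in 3b requires attribution.
2. Report the percentage of infants with IVIG-attributed SAEs and with IVIG-attributed grade 3 to 5 events beside the all-cause percentages, each with a one-sided 90% upper bound.
3. As supportive analysis, show START placebo SAE and grade 3 to 5 rates over the same days after HPE. Count first events up to transplant in both groups by cumulative incidence, and give a one-sided 90% upper bound on the difference. Do this only if START recorded and graded adverse events comparably, and state the open-label versus blinded difference beside the result.

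Items 1 and 2 need wording and tables from data this trial already collects. Item 3 needs extra analysis of START data and a check of how START recorded events. Its price is limited precision and possible ascertainment bias, so it should be presented as a background rate and not as a test. Attribution in an open-label trial is also a judgement, which is why the all-cause figures should stay in the report.

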# 4.3.2. Secondary Outcome Measures:

- 1. Percentage of subjects who survive 90 days after HPE with both their native liver and serum total bilirubin <1.5 mg/dL at 90 days after HPE. For this study, serum total bilirubin must be measured as a total and not calculated by summing bilirubin components (such as serum indirect plus direct bilirubin or conjugated plus unconjugated bilirubin).
- 2. Percentage of subjects who survive 180 days after HPE with both their native liver and serum total bilirubin <1.5 mg/dL at 180 days after HPE. For this study, serum total bilirubin must be measured as a total and not calculated by summing bilirubin components (such as serum indirect plus direct bilirubin or conjugated plus unconjugated bilirubin).
- 3. Percentage of subjects who survive 360 days after HPE with both their native liver and serum total bilirubin concentration <1.5 mg/dL at 360 days after HPE.
- 4. Percentage of subjects who survive with their native liver at 360 days after HPE.
- Percentage and absolute number of Tregs (CD4+CD25+FoxP3+), CD3/4 T cells, CD3/8 T cells, NK cells (CD56), NK T cells (CD3/56), CD19/20 B cells, macrophages (CD14/11b), and neutrophils; plasma levels of anti-enolase antibody; and plasma cytokine levels (Th1/Th2 multiplex and IL17) prior to IVIG dose #1 and at 60, 90, 180, and 360 days after HPE.

# 4.4. Study Design and Intervention

# 4.4.1. General Study Design

The primary objective of this study is to determine the feasibility, tolerability and safety of administering three doses of IVIG intravenously to 29 subjects with BA who have undergone the HPE surgery within 5 days prior to enrollment. Consent will be obtained, baseline clinical and research blood specimens will be obtained, historical and clinical data obtained, and IVIG will be administered at days 3-5, 30 and 60 days following HPE. When possible, peripheral venous catheters, central venous lines or peripherally inserted central catheters (PICC) lines that were placed for clinical indications will be used for the IVIG administration. Blood draws will be drawn through IV lines whenever possible. If no IV access is available, a peripheral IV will be placed for administration of IVIG and blood draws at the time of each IVIG infusion and removed after the infusion. Analysis of feasibility, tolerability and safety will be ongoing during this trial by the Safety Monitor, DSMB and NIH Project staff (see Section 7.6)

# 4.4.2. Recruitment for study

All infants with an established diagnosis of BA who are seen at one of the ChiLDREN study sites and who undergoes a standard surgical HPE before age 120 days will be eligible for the trial. Families of infants with a high suspicion of the diagnosis of BA will be approached and provided information about this trial either before the patient undergoes surgical exploration and the HPE surgery or within 3 days of the performance of HPE for the diagnosis of BA. In general, these infants were referred to the ChiLDREN site for clinical evaluation of cholestasis. Therefore, there will not be any specific advertising to increase referrals to the ChiLDREN sites for the purposes of this study.

# 4.4.3. Consenting for study

Written informed consent will be obtained within 3 days after HPE surgery performed for established biliary atresia. As part of the informed consent process, parents/legal guardians will be informed of the study procedures, the design of the study, the potential risks and benefits of participation and potential side effects of IVIG. This information will be shared with the parent/guardians at the time of enrollment.

# 4.4.4. Administration of study drug (IVIG)

IVIG will be administered on both an inpatient and outpatient\_basis. Reported adverse events and potential risks are described in Section 7. Appropriate adjustment to the IVIG infusion rate and early termination are described in Section 6. No investigational or commercial agents or therapies other than those described below may be administered with the intent to treat the subject's biliary atresia. If a subject has an acute illness at the time that an IVIG dose is due, the subject will be stabilized medically as per local standard of care before the dose of IVIG is administered. If the 30 day post-HPE visit is missed the 60 day post-HPE dose may still be administered.

Dose and timing: All participants will receive the same dose of IVIG at the same intervals in an open-label fashion as outlined in Table 2 as long as the subject does not have any increased risk for toxicity for any IVIG infusion (see Section 7.4). The day of the HPE will be considered the day that the surgery is completed (the day that the patient leaves the operating room) and this will be called Day 0. The first dose of IVIG will be given on Day 3-5 following the surgery while the subject is still in the hospital. Consent will need to be obtained before the first IVIG infusion.

IVIG will be initiated on day 3-5 after HPE surgery (HPE is day 0) at a dose of 1 gm/kg body weight by slow intravenous infusion over at least 4-8 hours, or according to local clinical guidelines for rate and time of infusion. The same dose (1 gm/kg) and duration of infusion will be repeated on day 30 and on day 60 after HPE. Ideally the first dose will be administered on day 3 after HPE, however the first dose may be administered on day 4 or 5 after HPE if there is a clinical situation that precludes start of the study medication on day 3. Dose #1 must be given while the subject is still hospitalized. Dose #2 and #3 may be given as outpatient infusions at the study site if the subject has been discharged from the hospital, as expected. The dose will be based on the weight of the subject on the day of the infusion. If the subject has an intercurrent illness or infection that would preclude giving the 2nd or 3rd IVIG dose at the specified times, the subject will be stabilized or treated for this illness and then the IVIG will be given if the investigator believes it will be tolerated. Since there is a 10 day window for administering doses #2 and #3 of IVIG, we anticipate that all doses will be able to be given during this window. If dose #2 is missed for reasons other than an IVIG related adverse event, dose #3 may still be given. Standard precautions will be taken for administering IVIG, including administering IVIG in a controlled setting by experienced nursing staff, and with the immediate availability of intravenous diphenhydramine, intravenous or subcutaneous epinephrine, and oral or rectal acetaminophen. Local site standard protocol for administration of IVIG will be followed, which may include premedication with acetaminophen or diphenhydramine.

A single dosage level of 1 gm/kg of IVIG was chosen for this study (rather than a range of escalating doses) because 1) this dose is effective and commonly used to treat other autoimmune or immune-mediated diseases in children and adults, 2) this dose can be administered intravenously over 6-8 hours during an outpatient research visit, and 3) this dose is usually not associated with significant side effects in children. To attempt to study several escalating doses in this study would imply that there was a therapeutic target for serum IgG that we would be trying to achieve and that the proper dose could be determined based on PK/PD studies. However, there is no target serum level of IgG that is

known to be effective for BA or for other diseases and, thus, PK/PD studies would be difficult to interpret. Therefore, we chose to use a high dose of IVIG that is effective in other immune-mediated diseases in children and adults and that should be well tolerated by the infants and their families.

Route of Administration: Dose #1 of IVIG will be administered through peripheral IV, central venous catheter or PICC line, whichever is in place for clinical indications on days 3-5 following HPE. It is mandatory that dose #1 be administered during the inpatient post-operative period following HPE. It is anticipated that doses #2 and #3 of IVIG will be administered in the outpatient setting, although these doses could be administered in the inpatient setting if the subject had been admitted to hospital for a clinically indicated reason. If no IV is in place at the prescribed time for doses #1, #2, or #3 of IVIG, then a peripheral IV will be started for the study drug administration and removed after administration of the IVIG. If the family does not allow placement of a peripheral IV for a dose of IVIG, then that dose of IVIG will not be given but the subject will remain in the study and follow the rest of the study protocol, including attempts at administering subsequent IVIG doses.

IVIG Infusion	Day of dosing following HPE*	IVIG dose**
#1	Day 3 (up to day 5)	1 gm/kg body weight
#2	Day 30	1 gm/kg body weight
#3	Day 60	1 gm/kg body weight

Table 2. Schedule and dosing of IVIG following HPE in infants with biliary atr	esia.
--	-------

\*See 4.4.4 Dose and Timing

\*\*Initial dose will be based on subject's weight at time of HPE. Subsequent doses will be adjusted based on subject's weight measured at 30 and 60 days after HPE. HPE = hepatic portoenterostomy; IVIG = intravenous immunoglobulin

